## **Exclusion Criteria**

### *For patients who completed study 16159A*

#### General

1. The patient has previously been screened in this study.
2. The patient is a member of the study personnel or of their immediate families, or is a subordinate (or immediate family member of a subordinate) to any of the study personnel.
3. The patient has developed a severe drug allergy or hypersensitivity to the IMP or its excipients during study 16159A.
4. The patient is, in the investigator's opinion, unlikely to comply with the protocol or is unsuitable for any reason.

#### Psychiatric

5. The patient has been diagnosed with a primary psychiatric disorder other than schizophrenia during study 16159A.
6. The patient has a clinically significant unstable illness diagnosed during study 16159A.
7. The patient is experiencing an acute exacerbation of his/her psychotic symptoms according to the investigator's clinical judgement.
8. The patient has a current diagnosis of substance use disorder according to DSM 5™ criteria during study 16159A with the exception of tobacco, or mild cannabis or mild alcohol use disorder. Patients with a positive drug screen test at the Baseline Visit, with the exception of cannabis and verified by repeated testing, are excluded from the study.
9. The patient, in the opinion of the investigator, is at significant risk of suicide, or the patient:

- Answers “Yes” to any question on the Suicidal Behaviour section of the C-SSRS, OR
  - Answers “Yes” to questions 4 and 5 on the Suicidal Ideation section of the C-SSRS.
10. The patient has started formal cognitive or behavioural therapy or systematic psychotherapy during study 16159A. Any ongoing formal psychotherapy initiated more than 6 weeks prior to Screening Visit of study 16 159A should be continued with the same methodology and at the same frequency and intensity during the entire study.
  11. The patient has experienced neuroleptic malignant syndrome during study 16159A.

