  - o. Prolactin results will remain blinded throughout the study.
  - p. For *16159A-patients*, additional ECGs will be done; 1 ECG recording before the daily dose is switched to weekly dosing (preferably on the day the decision of switching from daily to weekly dosing is taken) and 1 ECG recording the day after the first weekly dose is taken.
  - q. The first dose of IMP should be taken after the Baseline Visit is completed. All treatment assignment and subsequent IMP assignment is done via the IVRS/IWRS. The IVRS/IWRS will be assessed at the unscheduled visit only if the dose adjustment requires dispensing of IMP.
  - r. The dose of IMP can be increased for efficacy or decreased for tolerability at scheduled or unscheduled visits from Week 1 Visit.
  - s. For *16159A-patients* and *16323A-patients*, ongoing concomitant medication in study 16159A and 16323A, respectively, must be transferred by the investigators to the 16159B eCRF. All prescription, non-prescription medications, and herbal medications taken during study 16159B will be recorded as concomitant medications.
  - t. Urine drug screen tests can be repeated any time during the study at the discretion of the investigator.
  - u. S-βhCG pregnancy test should be performed at the Screening Visit (Only for *Other-patients*), Visit 5, Visit 10 and the Primary Outcome/Withdrawal Visit for women of childbearing potential. Urine pregnancy tests can be performed at any time during the study at the discretion of the investigator.

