**For patients who can potentially benefit from treatment with Lu AF35700**

General

1. The patient has previously been enrolled in this study.
2. The patient has participated in a clinical study <30 days prior to the Screening Visit.
3. The patient is a member of the study personnel or of their immediate families, or is a subordinate (or immediate family member of a subordinate) to any of the study personnel.
4. The patient is under forced treatment.
5. The patient is pregnant or breast-feeding.
6. The patient has a history of severe drug allergy or hypersensitivity, or known hypersensitivity to any of the IMP(s) or its/their excipients.
7. The patient has a disease or takes medication that could, in the investigator's opinion, interfere with the assessments of safety, tolerability, or efficacy, or interfere with the conduct or interpretation of the study.
8. The patient takes or has taken disallowed recent or concomitant medication (specified in [Appendix II](#)) or it is anticipated that the patient will require treatment with at least one of the disallowed concomitant medications during the study.
9. The patient is, in the investigator's opinion, unlikely to comply with the protocol or is unsuitable for any reason.

Psychiatric

10. The patient has any current psychiatric disorder (DSM-5™ criteria) other than schizophrenia established as the primary diagnosis.
11. The patient suffers from intellectual disability, organic mental disorders, or mental disorders due to a general medical condition (DSM-5™ criteria).
12. The patient is experiencing acute exacerbation of his/her psychotic symptoms at the Screening Visit, between the Screening and Baseline Visits or at the Baseline Visit according to the investigator's judgment.
13. The patient is treated with clozapine at the time of the Screening Visit.
14. The patient has a current diagnosis or a history of substance use disorder according to DSM-5™ criteria within 6 months prior to the Screening Visit with the exception of tobacco, or mild cannabis or mild alcohol use disorder. Patients with a positive drug screen test with the exception of cannabis and verified by repeated testing are excluded from the study.

15. The patient is at significant risk of harming himself/herself or others according to the investigator's clinical judgement, or who on the C-SSRS:
  - Answers "Yes" to questions 4 or 5 on the Suicidal Ideation section within the last 3 months at Screening, OR

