  - Answers "Yes" to any question on the Suicidal Behaviour section within the last 3 months at Screening, OR
  - Answers "Yes" to questions 4 or 5 on the on the Suicidal Ideation section at Baseline.
16. The patient has had neuroleptic malignant syndrome.
17. The patient has started formal cognitive or behavioural therapy or systematic psychotherapy within 6 weeks prior to Screening, or plans to start such therapy during the study. Any ongoing formal psychotherapy initiated more than 6 weeks prior to Screening should be continued with the same methodology and at the same frequency and intensity during the entire study.

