## 5.4 Withdrawal Criteria

A patient must be withdrawn from the study if:

- the patient and/or his or her legal representative (if applicable) withdraw(s) his or her consent (defined as a patient and/or his or her legal representative [if applicable] who explicitly take(s) back his or her consent); section 8.4 states how the patient's data will be handled
- the patient is lost to follow-up (defined as a patient who fails to comply with scheduled study visits or contact, who has not actively withdrawn from the study, and for whom no alternative contact information is available [this implies that at least two documented attempts have been made to contact the patient via both phone and mail]).

A patient must be withdrawn from treatment if:

- the investigator considers it, for safety, lack of efficacy, and/or study compliance reasons, in the best interests of the patient that he or she be withdrawn
- the patient becomes pregnant
- the patient has a serum ALT or AST value >3 times the upper limit of the reference range and a serum total bilirubin value >2 times the upper limit of the reference range
- the patient has a serum ALT or AST value >5 times the upper limit of the reference range that is confirmed by testing <2 weeks later
- the patient has a QTcF interval >500 ms or a change from Screening (or from Baseline for *16159A-patients* and *16323A-patients*) in the QTcF interval >60 ms concurrently with a QTcF interval >470 ms
- the patient has a positive urine drug screen verified by repeated testing at the following site visit
- the patient fails to comply with study procedures
- the patient is <80% IMP compliant between two consecutive, scheduled visits
- the patient in the opinion of the investigator has significant risk of suicide or who answers "Yes" to suicidal ideation questions 4 or 5 or answers "Yes" to suicidal behaviour on the C-SSRS® at any time during the study

Patients who withdraw will not be replaced.

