## 10 Adverse Events

### 10.1 Definitions

#### 10.1.1 Adverse Event Definitions

*Adverse event* – is any untoward medical occurrence in a clinical study patient administered a medicinal product and which does not necessarily have a causal relationship with this treatment.

An adverse event can therefore be any unfavourable and unintended sign (including clinically significant out-of-range values from relevant tests, such as clinical safety laboratory tests, vital signs, ECGs), symptom, or disease temporally associated with the use of a medicinal product, regardless of whether it is considered related to the medicinal product.

*Serious adverse event* (SAE) – is any adverse event that:

- results in death
- is life-threatening (this refers to an event in which the patient was at risk of death at the time of the event; it does not refer to an event that hypothetically might have caused death had it been more severe)
- requires inpatient hospitalisation or prolongation of existing hospitalisation
- results in persistent or significant disability/incapacity
- is a congenital anomaly/birth defect
- is medically important (this refers to an event that may not be immediately life-threatening or result in death or hospitalisation, but may jeopardise the patient or may require intervention to prevent any of the SAEs defined above)

Examples of medically important events are intensive treatment for allergic bronchospasm; blood dyscrasia or convulsions that do not result in hospitalisation; or development of drug dependency or drug abuse.

Planned hospitalisations or surgical interventions for a condition that existed before the patient signed the *Informed Consent Form* and that did not change in intensity are not SAEs. Emergency room visits that do not result in admission to the hospital are not necessarily SAEs; however, they must be evaluated to determine whether they meet any of the SAE definitions (for example, life-threatening or other serious [medically important] event).

The C-SSRS has 5 questions addressing suicidal ideation. If level 4 or 5 has been answered “yes”, it must be considered by the investigator whether an SAE should be reported.

*Non-serious adverse event* – is any adverse event that does not meet the definition of an SAE.

If there is any doubt as to whether an adverse event meets the definition of an SAE, a conservative viewpoint must be taken, and the adverse event must be reported as an SAE.

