12.6 Other Safety Endpoints(s)

12.6.1 Columbia-Suicide Severity Rating Scale (C-SSRS) Scores

Since no patients who had not previously participated in a study investigating Lu AF35700 were enrolled in study 16159B, only the *Since Last Visit Version* of the C-SSRS will be considered.

The C-SSRS was administered:

- at baseline (using the *Since Last Visit Version*) – the C-SSRS assessment at baseline that collects information since the previous visit. For 16159A patients this is the assessment performed at the Primary Outcome Visit of study 16159A and for 16323A patients this is the assessment performed at the last day of the dosing period in study 16323A.
- post-baseline (using the *Since Last Visit Version*) – the C-SSRS assessments after baseline

The C-SSRS scores post-baseline will be summarized based on the APTS. For the post-baseline assessments the score will be derived as the most severe item that the patient answered “Yes” to during the entire Treatment Period.

The definition of “most severe” is given by the ordering in [Panel 2](#).

The number and percentage of patients with *no suicidal ideation or behaviour* will be included in the summaries. Patients in this category are those who:

- answered ‘no’ to all ideation and behaviour questions; that is, answered ‘no’ to items 1 to 5 in [Panel 2](#) (related to suicidal ideation) and answered ‘no’ to items 6 to 10 in [Panel 2](#) (related to suicidal behaviour)

For the summary of the post-baseline scores, these patients will be the ones that at all assessments during the Treatment Period fulfilled this criterion.

Panel 2 C-SSRS Scores

C-SSRS Score		Related to:
1	Wish to be dead	Suicidal ideation
2	Non-specific active suicidal thoughts	
3	Active suicidal ideation with any methods (not plan) without intent to act	
4	Active suicidal ideation with some intent to act, without specific plan	
5	Active suicidal ideation with specific plan and intent	
6	Preparatory acts or behaviour	Suicidal behaviour
7	Aborted attempt	
8	Interrupted attempt	
9	Non-fatal suicide attempt	
10	Completed suicide (only applicable for the post-baseline assessments)	

Missing C-SSRS scores will not be imputed.

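### Roll-over patients can enter on a C-SSRS ideation answer that requires treatment to stop, and a verified drug-screen positive from a permitted benzodiazepine forces exclusion or withdrawal

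*Protocol*

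**What the plan says.** **C-SSRS ideation.** Protocol 5.3, criterion 9, excludes 16159A-patients who answer Yes to "questions 4 and 5 on the Suicidal Ideation section of the C-SSRS". The criterion for 16323A-patients is worded the same way, and so are the synopsis key exclusions for all three patient groups. The body criterion for Other Patients (criterion 15) differs: it excludes on "questions 4 or 5 on the Suicidal Ideation section within the last 3 months at Screening" and on "questions 4 or 5 on the on the Suicidal Ideation section at Baseline". Section 5.4 requires withdrawal from treatment, at any point in the study, of a patient who answers Yes "to suicidal ideation questions 4 or 5 or answers" Yes on suicidal behaviour. Section 10.1.1 also uses the either-question form: "If level 4 or 5 has been answered" Yes, the investigator has to consider whether to report an SAE.

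**Drug screen.** The urine panel includes benzodiazepines (Protocol 9.1.2 and Panel 4). Criterion 8 for both roll-over groups excludes a verified positive at Baseline, with cannabis the only exception. Section 5.4 requires withdrawal from treatment after a positive confirmed at the next site visit, with no exception. Appendix II allows anxiolytics and hypnotics received in 16159A to continue. For new anxiety rescue it recommends short-acting benzodiazepines and names lorazepam, oxazepam and alprazolam. Section 14 rules out waivers.

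**The concern.** An entry rule should not admit a patient on an answer that the withdrawal rule treats as a reason to stop. SAP Panel 2 defines ideation level 4 as "Active suicidal ideation with some intent to act, without specific plan", so the gap concerns active ideation with intent. Sites are given two thresholds for the same answer on the same scale.

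The drug-screen rules conflict in the opposite direction. They can remove a patient for taking something the protocol permits or recommends. The investigator holds the concomitant medication record (section 7), but no rule lets that record explain a positive. With waivers ruled out, a site must either exclude or withdraw such a patient, or deviate from the protocol.

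**Working it through.** The plan gives no figure on this point, so the check compares the rules and counts.

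**1. Ideation rules for a roll-over patient with no suicidal behaviour and no investigator-judged risk**

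| Q4 | Q5 | Excluded under criterion 9 (both)? | Withdrawn under 5.4 (either)? |
|---|---|---|---|
| No | No | no | no |
| Yes | No | **no** | **yes** |
| No | Yes | **no** | **yes** |
| Yes | Yes | yes | yes |

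Three patterns require withdrawal and the ideation part of criterion 9 catches one of them. This counts rule outcomes, not patients.

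**2. Timing.** Protocol Panel 2, note q, states: "The first dose of IMP should be taken after the Baseline Visit is completed". The Baseline C-SSRS answer is therefore available before exposure. If section 5.4 applies at Baseline, the patient is eligible and due for withdrawal at the same visit. If it applies only from the first dose, the patient is dosed on an answer that would stop treatment at any later visit.

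**3. Consistency of wording.** The both-questions form appears five times: three times in the synopsis and in criterion 9 for each roll-over group. The either-question form appears four times: twice in criterion 15, once in 5.4 and once in 10.1.1. The first three of these are entry or withdrawal rules; the last concerns SAE reporting. For Other Patients the synopsis and the body criterion contradict each other.

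**4. Reach of the ideation rule.** SAP 16 reports more than 500 patients. SAP 5 gives 4 from 16323A, and SAP 2 says Other Patients were never enrolled. Every enrolled patient therefore entered under the both-questions form. The C-SSRS is then scheduled at Visits 3 to 17, which is 17 − 3 + 1 = 15 visits, of which 14 precede the final visit. SAP 12.6.1 says: "The C-SSRS scores post-baseline will be summarized based on the APTS". No planned summary table shows how many patients entered with a single Yes.

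**5. Drug screen.** All three of the named new rescue drugs for anxiety are benzodiazepines.

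- At Baseline, a verified positive from a benzodiazepine continued from 16159A excludes the patient under criterion 8.
- On treatment, a verified positive from continued or rescue use requires withdrawal under 5.4.
- For roll-over patients Panel 2 schedules screens only at Baseline and at Week 52 or Withdrawal. None falls at the 16 − 3 + 1 = 14 visits between (Visits 3 to 16). On-treatment withdrawal therefore depends on tests the investigator orders (note t).

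**The case against.** The strongest reply on ideation is that other safeguards cover the gap. Criterion 9 also excludes anyone the investigator judges to be at significant suicide risk. Criterion 4 allows exclusion of a patient thought unsuitable on any ground. Section 10.1.1 makes the investigator consider an SAE report on a single Yes. If 5.4 covers Baseline, nobody with a single Yes is dosed. The word *and* may simply be loose drafting for either. These points narrow the gap, but the first three rest on judgement, whereas 5.4 is mandatory whatever the investigator thinks. If either was meant, the text still needs correcting.

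It can also be said that the cohorts are not comparable, because the Screening criterion for Other Patients looks back three months. That does not affect the main comparison. Under SAP 12.6.1, roll-over patients are rated at Baseline and afterwards on the same since-last-visit version.

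On the drug screen, the only scheduled post-baseline test falls when treatment is ending, so it cannot itself cause withdrawal from treatment. An investigator who orders an extra test already knows the medication. Appendix II permits continued anxiolytics in general, not benzodiazepines specifically, and names only 16159A. These limits stand and bear on frequency; the conflict in the rules remains.

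Three further points are fair. The two matters are separate and need separate edits. Cannabis is exempt at entry but not in 5.4, and whether to exempt it on study is a separate choice. Entry changes now come too late to alter who enrolled.

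**Conclusion.** Both contradictions hold as written and should be corrected. The ideation rule admits roll-over patients under two of the three answer patterns that require withdrawal, provided they report no suicidal behaviour and the investigator sees no significant risk. The drug-screen rules require exclusion or withdrawal for a verified positive caused by medication that Appendix II allows. The exclusion case is documented only for 16159A-patients whose continued anxiolytic is a benzodiazepine.

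The number of patients affected cannot be derived. The figure of more than 500 is everyone subject to the entry rule, not everyone harmed by it. How many reached Baseline with a single Yes, or on a benzodiazepine, depends on information these documents do not contain. This is a matter of patient safety and clear conduct. No effect on a primary endpoint summary is shown.

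**What to change.** **Ideation.** Replace *and* with *or* between questions 4 and 5 in criterion 9 for both roll-over groups and in the synopsis for all three groups. This aligns entry with section 5.4 and criterion 15.

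**Drug screen.** In criterion 8 for 16159A-patients and in section 5.4, add a clause such as: *a verified positive explained by recorded medication permitted under Appendix II does not count.* Add it to criterion 8 for 16323A-patients only if they too may continue anxiolytics, which Appendix II does not say. The cannabis wording can stay as it is.

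**Cost.** A short protocol amendment, with no new data and no SAP change. Entry becomes slightly stricter on ideation, and the investigator must check each positive against the medication record. Recruitment is past by the SAP's stage, so only the 5.4 change can help, and only for patients still on treatment.

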#### Medical

12. The patient has any other medical disease for which the treatment takes priority over treatment of schizophrenia or is likely to interfere with study treatment or impair treatment compliance.
13. The patient has a moderate or severe ongoing adverse event related to IMP from study 16159A considered of potential safety risk by the investigator.
14. The patient takes or has taken disallowed recent or concomitant medication (specified in [Appendix II](#)) in study 16159A.
15. The patient has a disease or takes medication that could, in the investigator’s opinion, interfere with the assessments of safety, tolerability or efficacy, or interfere with the conduct or interpretation of the study.
16. The patient has clinically significant abnormal vital signs considered of potential safety risk by the investigator.
17. The patient has one or more laboratory values outside the reference range, based on the last available blood or urine samples taken during study 16159A that are, in the investigator’s opinion, of potential risk to the patient’s safety, or the patient has any of the following values at study 16159A (the medical monitor should be contacted in case of uncertainty):
  - a serum creatinine value >1.5 times the upper limit of the reference range
  - a serum total bilirubin value >1.5 times the upper limit of the reference range
  - a serum alanine aminotransferase (ALT) or aspartate aminotransferase (AST) value >2 times the upper limit of the reference range
18. The patient has not previously been diagnosed with diabetes, but meets ANY of the following criteria (newly diagnosed diabetes) based on the last available blood samples taken during study 16159A:
  - HbA1C >6.5%, OR
  - fasting plasma glucose >126 mg/dL (7.0 mmol/L), OR
  - non-fasting plasma glucose >200 mg/dL (11.1. mmol).
19. The patient has previously been diagnosed with diabetes, but the condition is unstable as determined by ANY of the following criteria based on the last available blood samples taken during study 16159A:
  - HbA1c ≥7.0%, OR
  - glucose >6.94 mmol/L (fasting, >125 mg/dL) or 11.1 mmol/L (nonfasting, 200 mg/dL)

- any other abnormal laboratory tests that in the investigator’s clinical judgement are medically significant and would impact on the safety of the patient or the interpretation of the study results.
20. The patient has orthostatic hypotension (defined as a decrease in systolic blood pressure >20 mmHg between two measurements, first in the supine position and then sitting, and standing after the patient has rested in each position for at least 3 minutes.
  21. The patient has, based on the last available ECG measurement taken during study 16159A:
    - an abnormal ECG that is, in the investigator’s opinion, clinically significant
    - a PR interval >250 ms
    - a QRS interval >130 ms
    - a QTcF interval >450 ms (for men) or >470 ms (for women) (based on the Fridericia correction where  $QTcF = QT/RR^{0.33}$ )
    - A patient should also be excluded if he or she has any other abnormal ECG tests that in the investigator’s clinical judgement are medically significant and would impact the safety of the patient or the interpretation of the study results.

For patients who completed the dosing period of study 16323A

General

1. The patient has previously been enrolled in this study.
2. The patient is a member of the study personnel or of their immediate families, or is a subordinate (or immediate family member of a subordinate) to any of the study personnel.
3. The patient has developed a severe drug allergy or hypersensitivity to the IMP or its excipients during study 16323A.
4. The patient is, in the investigator’s opinion, unlikely to comply with the protocol or is unsuitable for any reason.

Psychiatric

5. The patient has been diagnosed with a primary psychiatric disorder other than schizophrenia during study 16323A.
6. The patient has a clinically significant unstable illness diagnosed during study 16323A.
7. The patient is experiencing an acute exacerbation of his/her psychotic symptoms according to the investigator’s clinical judgement.
8. The patient has a current diagnosis of substance use disorder according to DSM 5TM criteria during study 16323A with the exception of tobacco, or mild cannabis or mild alcohol use disorder. Patients with a positive drug screen test at the Baseline Visit, with the exception of cannabis and verified by repeated testing, are excluded from the study.
9. The patient, in the opinion of the investigator, is at significant risk of suicide, or the patient:
  - Answers “Yes” to any question on the Suicidal Behaviour section of the C-SSRS, OR
  - Answers “Yes” to questions 4 and 5 on the Suicidal Ideation section of the C-SSRS.

10. The patient has started formal cognitive or behavioural therapy or systematic psychotherapy during study 16323A. Any ongoing formal psychotherapy initiated more than 6 weeks prior to Screening Visit of study 16323A should be continued with the same methodology and at the same frequency and intensity during the entire study.
11. The patient has experienced neuroleptic malignant syndrome during study 16323A.

